However, the QSM validations and clinical correlations in CAs have been conducted at a single site to date, and DCEQP was applied to CAs at only two sites using slightly different protocols. FDA approved image acquisition sequences of QSM and DCEQP have been implemented on different MRI instruments from major manufacturers, but their validation at multiple sites have not been reported, nor specifically in CAs. The feasibility, accuracy, precision and reproducibility of biomarker measurements at multiple sites are critical to their potential application as outcomes instruments in clinical trials. We propose a rigorous approach to address these gaps in Specific Aim 2 of this project.

Knowledge Gaps Regarding Follow- and

Outcomes Assessment. Reducing the rate of recurrent SH as a clinical outcome would decrease the burden of disease, since a single SH can lead to devastating neurologic sequelae. This would be an approvable outcome, adjudicated, readily defined and easy to measure. Yet there are many knowledge gaps and potential obstacles to planning clinical trials based on this primary outcome. Attempting to power a study

Table. Power Calculation Models

Numbers of patients needed, based on different re-bleed rates. Calculated by Parexel, 90% power, 1-sided, Type 1 error 0.025, treatment allocation 1:1, dropout rate 10%.

Annual rate of SH in control	Follow-up period	Reduction in SH rate (%)	Sample size/group
6%	1.5 yrs	25%	3341
	1.5 yrs	50%	720
15%	1.5 yrs	25%	1161
	1.5 yrs	50%	253
30%	1.5 yrs	25%	435
	1.5 yrs	50%	98

based on recurrent SH would require at least a 1- to 2-year study and a significant number of patients (Table). The relative mix of lesions with different re-bleed rates will greatly influence the sample size needed to show treatment effect based on this primary outcome. Limiting trials to brainstem lesions would enhance statistical power, but also restrict recruitment and prevent generalizability of a drug's effects to other CASH cases that could benefit. Other studies suggest an equally high rate of SH in deep supra-tentorial and possibly cerebellar CAs²¹. **The rates of recurrent SH have never been assessed prospectively at multiple sites in CASH trial candidates.**

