Specific Aim 3. Time to recurrent SH will be analyzed using Kaplan Meier method and Cox proportional hazards regression approach. Rates of recurrent SH/patient/year from initial SH qualifying event, and SH/patient/year from enrollment (potentially more relevant for trial modeling) will be estimated along with 95% CIs. Changes in mean lesional QSM and K_i during 1 and 2-year epochs will be compared using paired t-test or Wilcoxon signed rank test to assess changes within patients over time, including 95% CIs. To test predictive, monitoring or surrogate outcome hypotheses, two sample t-test or Wilcoxon rank sum test will be used to compare such changes between patients with and without recurrent SH. Categorical variables such as proportions of patients with a drop in mRS score ≥ 1 point, difference in EQ-5D and PROMIS 29 scores, NIHSS scores, between patients with and without recurrent SH will be compared using Chi-square or Fisher's exact test. Associations of baseline characteristics (sex, lesion locations, familial/sporadic) and recurrent SH as a binary outcome (yes/no) will be assessed using

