univariable and multivariable logistic regression and reported as odds ratios and 95% CIs. Depending on the number of recurrent SH over the 2-year period, we may analyze re-bleeds as a continuous outcome and the associations of baseline features or biomarkers assessed using linear regression. Performance of final model(s) will be assessed using r^2 in the case of linear regression, area under the curve (AUC) and Hosmer Lemeshow goodness of-fit test⁵⁵ in the case of logistic regression, or concordance index in the case of Cox proportional hazards regression. AUCs between various models (univariable) will be compared using the method proposed by DeLong et al⁵⁶. For biomarkers, we will create a binary variable (yes/no) depending on whether the % change in mean lesional QSM or K_i during 1-year epochs exceed previously defined respective thresholds (+ 5.8% QSM and +39.6% for K_i)³³ that were significantly associated with new clinical events at high sensitivity and specificity in previously stable lesions. We will then assess the association of this newly created variable (“biomarker event”) with SH rate treated as continuous (using two sample t-test or Wilcoxon rank sum test) and binary (using Chi-square or Fisher’s exact test) outcomes of interest. Finally, we shall compare the sensitivity/specificity of changes in mRS, QOL, and NIHSS scores, and lesional QSM and K_i in relation to SH during the same epochs, using McNemar’s test with SH (yes/no binary) as the reference standard. All tests will be 2-sided and p-values <0.05 considered statistically significant.

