Follow-up and Biomarker Validation (FUBV) Sites: University of Chicago, University of New Mexico, Mayo, University of California San Francisco, and Johns Hopkins were chosen because of additional established infrastructure for advanced imaging, including identified MRI physicists, neuroradiologists and site engineers who will work with the Biomarker Imaging Core (BIC) on implementing QSM and DCEQP protocols. A subset of approximately 120 CASH cases will be enrolled at FUBV sites to perform imaging biomarker validation studies (Specific Aim 2) and follow-up of CASH cases annually for up to two years (Specific Aim 3) to evaluate changes in outcomes. This subset of CASH cases will undergo a research MRI scan at baseline and at 1 and 2-year follow-up visits and undergo modified Rankin Scale (mRS) score and EQ-5D, PROMIS 29, and NIHSS assessments. A target recruitment of 120 CASH cases over 3-4 years at the sites conducting the FUBV arm is amply justified, with demonstrated 256 CA cases recently evaluated per year at those sites, expecting to identify 38 CASH cases each year (15% prevalence). Utah and Barrow may also serve as alternate FUBV arm sites if needed, with large demonstrated CA clinical activity. The University of California San Francisco and Johns Hopkins are now part of the FUBV arm.

Assuming a sample size of 120 CASH cases, and allowing 30% dropouts or missing biomarker or other data, we would have 84 evaluable patients (168 patient-years). We project 10%-20% re-bleed rate/year, supported by population studies and meta-analyses of CASH^{18, 19}, with the higher estimate particularly applying to brainstem cases. We would hence expect 17-34 SHs. Based on this, for continuous outcomes we will have 80% power at an alpha level of 0.05, to detect a difference between the means of patients with and without re-bleeding of at least 0.63-0.77 standard deviation. For categorical outcomes (i.e. presence or absence of a risk factor) we will be able to detect a difference of 32-40% between these two groups. This allows testing of questions regarding the rate of SH, and the prevalence of other outcomes in relation to SH during follow-up (Specific Aim 3).

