9.4 STATISTICAL ANALYSES

9.4.1 GENERAL APPROACH

Data collection. Key variables to be collected in this study will be decided on by all stakeholders in Year 1. At a minimum, these will include patient demographics, genotype, baseline MRI lesion features of the hemorrhagic CA (size, location), time from SH, prior bleeds/dates, and diagnosis date. Functional status will be measured using the modified Rankin Scale (mRS) score⁵⁷, Euro-QoL⁵³, PROMIS29⁵², and NIH Stroke Scale. PROMIS 29 short forms are an assessment of anxiety, depression, and fatigue, and have been validated for use in several common neurological disorders. Presence of obstructive sleep apnea. Recent findings suggest that sleep apnea results in decreased blood flow to the brain. This transient ischemia may be implicated in CA hemorrhage. Sleep apnea questions will be included in the dataset and response analyses as described under the topic Predictors of SH.

Data harmonization. Common data elements from each site will be reviewed, updated, and harmonized using an iterative, stepwise process based on DataSHaPER (DataSchema and Harmonization Platform for Epidemiologic Research) recommendations⁵⁸⁻⁶⁰. Questionnaires, codebooks, and protocols, etc. at the 3 established CA databases (Table 2) will be compiled and distributed for review. A series of Executive Committee teleconference calls will be held in Year 1 to decide on a set of 'target' data elements for potential clinical trials, as has been similarly done with the consensus process for developing clinical guidelines paper¹⁷. The EDHC and DCC will then develop standardized electronic data entry forms and codebooks for data collection. Each site shall be trained in abstracting and entering data for their cases online. Data will be collected prospectively in Years 2-5. Analysis datasets will be generated quarterly by the DCC for quality control analysis by EDHC.

Event Rate: Time to recurrent SH will be analyzed using Kaplan Meier method and Cox proportional hazards regression approach. Rates of recurrent SH/patient/year from initial SH qualifying event, and SH/patient/year from enrollment (potentially more relevant for trial modeling) will be estimated along with 95% CIs.

Biomarker changes over 2 years: Changes in mRS, EQ-5D, PROMIS 29, and NIHSS scores, mean lesional QSM and K_i during 1 and 2-year epochs will be compared using paired t-test or Wilcoxon signed rank test to assess changes within patients over time, including 95% CIs.

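### At the plan's low expected count of 17 hemorrhages, logistic regression on its listed predictors can return an infinite or zero odds ratio, and no sparse-data method is named

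*Combined protocol and SAP*

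**What the plan says.** Section 9.1 (Specific Aim 3), repeated in Section 9.4.1 under predictors of SH (symptomatic hemorrhage), names the covariates and the outcome: "Associations of baseline characteristics (sex, lesion locations, familial/sporadic) and recurrent SH as a binary outcome (yes/no". The method is "univariable and multivariable logistic regression and reported as odds ratios and 95% CIs".

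Section 9.4.1 adds a further candidate: "Sleep apnea questions will be included in the dataset and response analyses as described under the topic Predictors of SH".

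Section 9.2 sets the information available. From 120 enrolled patients, "allowing 30% dropouts or missing biomarker or other data, we would have 84 evaluable patients (168 patient-years"). On the rate: "We project 10%-20% re-bleed rate/year". The result: "We would hence expect 17-34 SHs".

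The only provision tied to the event count is that re-bleeds may be treated as a continuous outcome in a linear regression. No section names a penalized, exact or Bayesian fit, a limit on the number of coefficients, a location coding, or a rule for merging small groups. Cox regression is listed for time to SH, also without a sparse-data provision.

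**The concern.** Logistic regression needs both outcomes in every covariate group. If one location has no recurrent SH, the maximum-likelihood log odds ratio for that location has no finite value. Software then prints a very large coefficient with a huge standard error, and the Wald interval is useless. This is separation. It becomes likely when events are few and a group is small. The linear-regression alternative does not help, because it does not produce the odds ratios the plan promises.

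Section 9.3 intends the predictor models to inform a covariate-adaptive randomization scheme for a Phase III trial. Section 4.2 says the mix of lesions with different re-bleed rates strongly affects sample size, and adds: "Other studies suggest an equally high rate of SH in deep supra-tentorial and possibly cerebellar CAs". If those locations are kept as separate groups, the smaller ones are where the stated method is most likely to fail. An analyst would then have to drop or merge a group, or change method, after seeing the data.

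**Working it through.** **1. The plan's own figures.** 120 x 0.70 = 84 patients; 84 x 2 = 168 patient-years; 168 x 0.10 = 16.8 and 168 x 0.20 = 33.6, so 17-34 SHs. The detectable differences in Section 9.2 also reproduce: a two-sample t-test (two-sided 0.05, 80% power) gives 0.770 SD for 17 v 67 patients and 0.630 SD for 34 v 50. The inputs are therefore as the plan intends.

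**2. Patients with an event.** The 17 counts hemorrhages. The binary outcome counts patients: 84 x (1 - 0.90²) = 84 x 0.19 = 16.0 at 10% per year.

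**3. Events per coefficient at 17 SHs.** Sex and familial status take one coefficient each; location with k groups takes k - 1.
- Two groups: 17/3 = 5.7
- Three groups: 17/4 = 4.3
- Four groups: 17/5 = 3.4
- Four groups plus sleep apnea: 17/6 = 2.8

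**4. Exact check of one sparse coding.** The shares are assumptions, because the documents give none. Take brainstem/deep/cerebellar/other at 35/15/10/40% of 84, that is 29/13/8/34 patients. P(at least one location without SH) = 1 - product of [1 - (1 - risk)^n].
- Two-year risk 0.20 everywhere: the two small groups have 0.80^13 = 0.055 and 0.80^8 = 0.168; the total is 22%.
- Risk 0.30 in brainstem and 0.15 elsewhere: 0.85^13 = 0.121 and 0.85^8 = 0.272; the total is 36%.

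**5. Simulation.** 84 patients, about 16 re-bleeders, sex 50%, familial 25% (Section 2.2 gives 20-30%), 1,500 runs per scenario. Separation means that any coefficient diverged. Each range covers repeated simulations and runs from equal risk to a brainstem odds ratio of 2.5, except the sleep apnea row, which uses 2.5.

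| Location coding (assumed shares) | Studies with separation |
|---|---|
| Four groups, 35/15/10/40% | 28-47% |
| Four groups, 30/20/15/35% | 14-25% |
| Three groups, 40/20/40% | 6-13% |
| Two groups | about 2% |
| Two groups plus sleep apnea at 10% prevalence | about 25% |

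With sleep apnea at 15% or 5% prevalence the last row becomes about 10% or 45%. The residual 2% with two location groups comes mainly from the familial group: 0.25 x 84 = 21 patients, and 0.80^21 = 0.9% even when its size is fixed.

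**6. Toward the high end.** At about 30 re-bleeders, separation falls to about 5-14% with four groups at 35/15/10/40%, and to a few percent or less with the more even four-group mix.

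**7. What Firth estimation does.** Estimates were finite in every run fitted. The mean brainstem log odds ratio was 0.89-0.94 against a true ln(2.5) = 0.92. It does not restore precision. At 17 events the median upper/lower ratio of the widest location 95% interval (Wald) is about 9 with two groups, 21 with three, and 30 to 71 with four (smallest group 25% down to 10%).

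**The case against.** **The frequency depends on a coding the documents do not give.** A reader might infer that 17 events alone make a location odds ratio often infinite. The documents do not support that. Section 4.2 mentions deep supratentorial and cerebellar lesions when reporting other studies; it does not define an analysis variable. Sections 2.1 and 2.2 pair deep with brainstem lesions, and Section 9.2 singles out brainstem only. Two or three groups fit the text at least as well as four, and even four equal groups give only about 3% at 17 events. This stands, and the conclusion is conditional for that reason.

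**Seventeen is the pessimistic end.** It combines the lowest rate with the full 30% loss, part of which is missing biomarker data that these covariates do not need. Data before attrition are kept (Sections 4.3 and 7.2). With all 120 patients at 10% per year, 120 x 2 x 0.10 = 24 SHs are expected, and the exact check with groups of 42/18/12/48 falls to 9% and 19%. This stands, although 17 is an expected value and the actual count could also be lower.

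**The plan does not exclude Firth.** It names logistic regression without a fitting method, does not say that every covariate enters together, and foresees refinement by the statisticians in Year 1 (Section 10.1.4). That is fair, but an unspecified fit will ordinarily be run as maximum likelihood, and the choice should not wait for the results.

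**The consequence is limited.** These odds ratios are not the sole basis for Phase III stratification: Section 9.3 also draws on imaging, clinical and biomarker data, and Section 9.4.2 reports re-bleed rates by location. Separation is visible in the output, and a profile-likelihood interval would still give a one-sided bound. The primary endpoint is unaffected. All of this stands. It lowers the priority but does not supply the estimates the plan promises.

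**Conclusion.** The point holds in conditional form. At the plan's low expected count, with about 3-6 SHs per coefficient, the stated regression can give an infinite or zero odds ratio without a usable interval, and nothing in the plan covers that case. How often depends on the assumed coding and shares: roughly 15-45% of studies with four location groups and the smallest at 10-15%, 6-13% with three, and about 2% with two unless a sparse covariate is added. Collapsing location therefore does not remove the risk by itself if sleep apnea enters the same model, which Section 9.4.1 allows but does not state.

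Two stronger readings should be avoided: that failure is the usual outcome whatever the coding, and that penalized estimation would make the predictors well estimated. Neither is supported. This is a cheap improvement to a secondary analysis, not a flaw in the primary one.

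**What to change.** In Sections 9.1 and 9.4.1:

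- State that the predictor models, logistic or Cox, are fitted by Firth penalized likelihood, and that odds or hazard ratios are reported with profile-penalized-likelihood 95% intervals.
- Pre-specify a location coding of two or three groups for the multivariable model, before outcome data are examined. Finer location groups can still be described through the subgroup rates of Section 9.4.2.
- State that at the low event count the intervals will be wide, and that the method secures finite, less biased estimates rather than precision.

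The cost is a few sentences and a standard software option; no new data are needed. The downside is slight shrinkage of large odds ratios toward 1, and some loss of location detail in the multivariable model.

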9.3 POPULATIONS FOR ANALYSES

Cavernous angiomas with symptomatic hemorrhage (CASH) are most likely to re-bleed and cause further neurologic sequelae. It would be desirable to develop a drug that stabilizes CASH, and prevent recurrent bleeding. CASH with recent bleed, where surgical resection is not undertaken, are the most likely cases to be followed expectantly per current evidence based guidelines, with clinical equipoise for testing novel therapies to prevent re-bleeding. They are the most likely cases to be targeted for clinical trials.

Appropriate and complete statistical modeling of data collected by the sites for both SCA/FUBV arms are imperative to the planning, development, and completion of a successful Phase III interventional trial. The most critical component is the accurate assessment of the enrollment rates of CASH across several sites, as well as the between-site variability in these estimates. Both within and between sites variability will be used to adequately power a Phase III trial, will be calculated by developing random-effect models along with using appropriate link functions quantifying the rates of CASH in these models.

As a follow-up step, in-depth data analyses will be performed using the demographic, imaging, clinical and biomarker data collected. These are applied to develop models assessing how predictive each of these factors is to the development of recurrent SH. Understanding which factors are most predictive of SH will be crucial in developing a covariate adaptive randomization scheme for the Phase III trial that insures proper balance in these prognostic factors between treatment arms. Finally, statistical assessments of changes in lesional iron content and permeability biomarkers, QOL, mRS, and NIHSS during follow-up of CASH patients will be performed. Understanding how these measures change over time will be an important step in the process of developing hypotheses on the effect of treatment on these as putative secondary or surrogate outcomes, or as potential composite outcomes.

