Predictors of SH: Two sample t-test or Wilcoxon rank sum test will be used to compare such changes between patients with and without recurrent SH. Categorical variables such as proportions of patients with a drop in mRS score ≥ 1 point, between patients with and without recurrent SH will be compared using Chi-square or Fisher's exact test. Associations of baseline characteristics (sex, lesion locations, familial/sporadic) and recurrent SH as a binary outcome (yes/no) will be assessed using univariable and multivariable logistic regression and reported as odds ratios and 95% CIs. Depending on the number of recurrent SH over the 2-year period, we may analyze re-bleeds as a continuous outcome and the associations of baseline features or biomarkers assessed using linear regression. Performance of final model(s) will be assessed using r^2 in the case of linear regression, area under the curve (AUC) and Hosmer Lemeshow goodness of-fit test⁵⁵ in the case of logistic regression, or concordance index in the case of Cox proportional hazards regression. AUCs between various models (univariable) will be compared using the method proposed by DeLong et al⁵⁶. For biomarkers, we will create a binary variable (yes/no) depending on whether the % change in mean lesional QSM or K_i during 1-year epochs exceed previously defined respective thresholds (+ 5.8% QSM and +39.6% for K_i) that were significantly associated with new clinical events at high sensitivity and specificity in previously stable lesions³³. We will then assess the association of this newly created variable ("biomarker event") with SH rate treated as both continuous (using two sample t-test or Wilcoxon rank sum test) and binary (using Chi-square or Fisher's exact test) outcomes of interest. Finally, we shall compare the sensitivity/specificity of changes in mRS, QOL, and NIHSS scores, and lesional QSM and K_i in relation to SH during the same epochs, using McNemar's test with SH (yes/no binary) as the reference standard. All tests will be two-sided and p-values <0.05 considered statistically significant.

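### Model performance for recurrent SH (AUC, c-index, r²) is planned without internal validation, so with 17-34 expected SHs the reported whole-model figures will be biased upward

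*Combined protocol and SAP*

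**What the plan says.** Section 9.1 (Specific Aim 3) and the Predictors of SH text in section 9.4.1 plan the same modelling. "Associations of baseline characteristics (sex, lesion locations, familial/sporadic) and recurrent SH as a binary outcome (yes/no) will be assessed using univariable and multivariable logistic regression", with odds ratios and 95% CIs. Cox regression is planned for time to recurrent SH, and linear regression may be used if there are enough re-bleeds. Final models are assessed by r² (linear), "area under the curve (AUC) and Hosmer Lemeshow goodness of-fit test" (logistic) or the concordance index (Cox). AUCs of univariable models are compared by the DeLong method.

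The predictor pool is wider than the three named factors. Section 9.4.1 adds sleep apnea questions to the Predictors of SH analyses. Section 9.3 extends the modelling to demographic, imaging, clinical and biomarker data, and states the purpose: "Understanding which factors are most predictive of SH will be crucial in developing a covariate adaptive randomization scheme for the Phase III trial".

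On size, section 9.2 says: "Assuming a sample size of 120 CASH cases", "allowing 30% dropouts or missing biomarker or other data". That leaves 84 evaluable patients and 168 patient-years. "We project 10%-20% re-bleed rate/year", and "We would hence expect 17-34 SHs".

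No section mentions bootstrap, cross-validation, a split sample, an external cohort, shrinkage, a limit on the number of predictors, or a rule for arriving at a final model.

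**The concern.** A model scored on the patients used to fit it looks better than it will in new patients. The gap grows as events per parameter fall. The plan does not say in words that the same data will be used, but it names no other data and no resampling. Section 1.3 gives SCA participants a baseline visit only, so the study holds no second cohort with outcomes. As written, the AUC, c-index and r² will be apparent values.

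This is more than a missing detail, because the figure that the stated analysis produces is biased. It is meant to inform which covariates enter a Phase III randomization scheme (section 9.3), and the milestones in section 10.1.2 include decisions on stratification. A Phase III team that reads an apparent AUC near 0.70 as a property of the disease could believe it has a prognostic model when it has none.

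**Working it through.** **1. The plan's event count (section 9.2).**
- Evaluable patients: 120 × (1 − 0.30) = 84. Follow-up: 84 × 2 = 168 patient-years.
- SHs: 168 × 0.10 = 16.8 and 168 × 0.20 = 33.6, which gives the stated 17-34.
- The stated detectable difference of 0.63-0.77 SD also reproduces (two-sided 0.05, 80% power, 17 v 67 and 34 v 50 patients). The normal approximation (1.96 + 0.84) × √(1/17 + 1/67) gives 0.76, and 0.62 for 34 v 50. The noncentral t gives 0.770 and 0.630.
- The logistic outcome is a patient with at least one SH, and there are slightly fewer of these: 84 × (1 − 0.9²) = 16 and 84 × (1 − 0.8²) = 30. Using 17 and 34 below is therefore mildly generous to the plan.

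**2. Number of parameters (not stated, so a range).**
- Named baseline set: sex 1 + location 2 (three levels assumed) + familial/sporadic 1 = 4 df.
- Assumed 7 df: the above plus sleep apnea, QSM and K_i.
- Assumed 12 df: a fuller draw on the section 9.3 pool.
- Events per parameter at 17/34 events: 4 df, 4.2/8.5; 7 df, 2.4/4.9; 12 df, 1.4/2.8.

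**3. Apparent AUC when nothing predicts.** Simulated datasets had n = 84, 17 or 34 events and true AUC 0.50. A logistic model was fitted and scored on the same data. Assumed predictor distributions: sex 50%, familial 25%, location 40/20/40, and continuous predictors independent standard normal. Mean AUC in new patients was 0.50.

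| Model | Mean apparent AUC, 17 / 34 events | Chance of apparent AUC ≥ 0.70, 17 / 34 events |
|---|---|---|
| One pre-specified predictor | 0.56 / 0.54-0.55 | about 1% or less |
| 4 df (named set) | 0.64 / 0.62 | about 13% / 2-4% |
| 7 df (assumed) | 0.70 / 0.66 | about 47% / 22% |
| 12 df (assumed) | 0.76 / 0.72 | about 88% / 64% |

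**4. Other measures under the same null.**
- Cox concordance at 10%/20% per year: 4 df 0.64/0.60; 8 df 0.70/0.65; 12 df 0.75/0.68.
- Linear r²: the expected value with k no-value predictors is k/(n − 1). That is 4/83 = 0.05, 7/83 = 0.08 and 12/83 = 0.14.
- Hosmer-Lemeshow gave p > 0.05 in about 95% of no-value models with 8-12 df, so it does not flag the overfit.
- Best of 12 no-value single predictors: mean AUC 0.65 (17 events) and 0.63 (34 events). Univariable AUCs stay near the truth only if the predictor is not picked for being the best.

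**5. When there is some signal.** With true AUC 0.65, 7 df and about 17 events, apparent AUC averages 0.74-0.75, while the fitted model's AUC in new patients is 0.58.

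**6. What the bootstrap recovers.** On pure noise, optimism correction brings the step 3 means down to about 0.54-0.59. In one small run (80 datasets, 60 resamples each), 12 df with 17 events was left at 0.61. Most of the optimism goes, but not all of it.

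**7. Individual tests.** In the null simulations at 4 and 7 df, a coefficient's Wald test rejected in about 4-5% of cases, close to its nominal 5%.

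**The case against.** A reader might infer more than the documents support, and on several counts the defence is right.

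- **That following the plan would endorse useless predictors.** It would not do so by any stated rule. The plan sets no AUC or c-index threshold for adopting a factor. It reports odds ratios with CIs and tests at two-sided 0.05, and those tests keep their error rate (step 7). The one planned AUC comparison is between univariable models, where a pre-specified predictor shows little optimism. The biomarker-change thresholds (+5.8% QSM, +39.6% K_i) come from an earlier study and carry none of this bias.
- **That Hosmer-Lemeshow makes worthless predictors look useful.** It cannot, because it tests calibration. Its limit here is that a non-significant result says nothing against overfitting.
- **That an apparent AUC of 0.70 from noise is what to expect.** That needs about 7 df, which is an assumption. The named set, at about 4 df, gives 0.62-0.64.
- **Denominator.** The figure of 84 allows for missing biomarker data, which the baseline model does not need, and data before attrition are kept (sections 4.3 and 7.2). With 120 patients and 24 events, 4 df of noise still gives about 0.62.
- **Consequence.** Balancing a future randomization on a non-prognostic factor does not bias its treatment comparison. Section 10.1.4 has statisticians refine the plans in year 1, and section 10.1.5 gives an advisory committee review of emerging data.

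These points limit the size and the consequence. They do not supply validation: none of those provisions mentions it, and the figures to be reported remain apparent ones.

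**Conclusion.** The concern holds for the whole-model performance figures. With no internal validation and no second outcome cohort, the AUC, c-index and r² in sections 9.1 and 9.4.1 will be biased upward. For predictors of no value the mean apparent AUC is about 0.62-0.64 on the named baseline set. It is 0.66-0.70 at 7 df and 0.72-0.76 at 12 df, both assumed, against a true 0.50. The direction does not depend on the parameter count, but the size does, and the plan leaves that count open. The figures also rest on the plan's own 84 patients and 17-34 SHs and on the simulated predictor distributions. The primary SH rate, the individual odds-ratio tests and the pre-set biomarker thresholds are outside the concern. It should be corrected because it is cheap to do so and the result informs Phase III design.

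**What to change.** In sections 9.1 (Specific Aim 3) and 9.4.1 (Predictors of SH):

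1. Report bootstrap optimism-corrected AUC, c-index and r², with a calibration slope, and repeat any variable selection inside each resample.
2. Fix a short candidate list, with its degrees of freedom, before analysis.
3. Fit the multivariable model with penalisation (ridge or Firth). Items 2 and 3 are needed because the bootstrap alone leaves some optimism at this number of events (step 6).
4. Hosmer-Lemeshow may stay, with a sentence that a non-significant result is not evidence against overfitting.

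The cost is SAP text and analysis code, with no new patients, visits or data. The reported AUC will be less favourable.
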